1.2.2 Tamsulosin Hydrochloride

Tamsulosin hydrochloride was registered in Japan in 1993, in the European Community in 1995 and in the USA in 1997. In the US, tamsulosin hydrochloride is indicated for treatment of the signs and symptoms of BPH and in the EU, for lower urinary tract symptoms (LUTS) associated with BPH. Since the launch of tamsulosin hydrochloride, a worldwide exposure of more than 24 million patient years has demonstrated that tamsulosin hydrochloride is effective and safe in the treatment of LUTS associated with BPH. The most common adverse event is dizziness and weakness. Intra-operative Floppy Iris syndrome during cataract and glaucoma surgery has been associated with tamsulosin hydrochloride use. The initiation of tamsulosin hydrochloride in patients with scheduled cataract or glaucoma surgery is not recommended (see US Package Insert, 2014 and EU SmPC, 2013).

1.2.2.1 Summary of Non-clinical Studies of Tamsulosin Hydrochloride

Tamsulosin hydrochloride is an antagonist of α_{1A} adrenoceptors in the prostate. The symptoms associated with benign prostatic hyperplasia (BPH) are related to bladder outlet obstruction, which is comprised of two underlying components: static and dynamic. The static component is related to an increase in prostate size caused, in part, by a proliferation of smooth muscle cells in the prostatic stroma. However, the severity of BPH symptoms and the degree of urethral obstruction do not correlate well with the size of the prostate. The dynamic

component is a function of an increase in smooth muscle tone in the prostate and bladder neck leading to constriction of the bladder outlet. Smooth muscle tone is mediated by the sympathetic nervous stimulation of α_1 adrenoceptors. Antagonism of these adrenoceptors can cause smooth muscles in the bladder neck and prostate to relax, resulting in an improvement in urine flow rate and a reduction in symptoms of BPH.

Tamsulosin hydrochloride, an α_1 adrenoceptor blocking agent, exhibits selectivity for α_1 receptors in the human prostate. At least three discrete α_1 adrenoceptor subtypes have been identified: α_{1A} , α_{1B} , and α_{1D} ; their distribution differs between human organs and tissue. Approximately 70% of the α_1 receptors in the human prostate are of the α_{1A} subtype.

1.2.2.2 Summary of the Pharmacokinetics of Tamsulosin Hydrochloride

The pharmacokinetics of tamsulosin hydrochloride have been evaluated in adult healthy volunteers and patients with BPH after single and/or multiple administration with doses ranging from 0.1 mg to 1 mg. Absorption of tamsulosin hydrochloride from capsules of 0.4 mg is essentially complete (90%) following oral administration under fasting conditions. Tamsulosin hydrochloride exhibits linear kinetics following single and multiple dosing, with achievement of steady-state concentrations by the fifth day of a once-a-day dosing. The time to maximum concentration (T_{max}) is reached by 4 to 5 hours under fasting conditions and by 6 to 7 hours when administered with food. Taking capsules under fasted conditions results in a 30% increase in bioavailability (AUC) and 40% to 70% increase in peak concentrations (C_{max}) compared to fed conditions.

Tamsulosin hydrochloride is extensively metabolized by cytochrome P450 enzymes in the liver and less than 10% of the dose is excreted in urine unchanged. However, the pharmacokinetic profile of the metabolites in humans has not been established. In vitro results indicate the CYP3A4 and CYP2D6 are involved in the metabolism of tamsulosin hydrochloride as well as some minor participation of other CYP isoenzymes. Inhibition of hepatic drug-metabolizing enzymes may lead to increased exposure to tamsulosin hydrochloride.

1.2.2.3 Summary of Clinical Data with Tamsulosin Hydrochloride

Four placebo-controlled clinical studies and one active-controlled clinical study enrolled a total of 2296 patients (1003 received 0.4 mg capsules tamsulosin hydrochloride once daily, 491 received 0.8 mg capsules tamsulosin hydrochloride once daily, and 802 were control patients) in the US and Europe.

In the two US placebo-controlled, double-blind, 13-week, multi-center studies [Study 1 (US92-03A) and Study 2 (US93-01)], 1486 men with the signs and symptoms of BPH were enrolled. In both studies, patients were randomized to either placebo, tamsulosin hydrochloride capsules 0.4 mg once daily, or tamsulosin hydrochloride capsules 0.8 mg once daily. Patients in tamsulosin hydrochloride capsules 0.8 mg once daily treatment groups received a dose of 0.4 mg once daily for one week before increasing to the 0.8 mg once daily dose. The primary efficacy assessments included: 1) total American Urological Association

(AUA) Symptom Score questionnaire, which evaluated irritative (frequency, urgency, and nocturia), and obstructive (hesitancy, incomplete emptying, intermittency, and weak stream) symptoms, where a decrease in score is consistent with improvement in symptoms; and 2) peak urine flow rate, where an increased peak urine flow rate value over baseline is consistent with decrease urinary obstruction.

Mean total AUA Symptom Scores for both tamsulosin hydrochloride capsules 0.4 mg and 0.8 mg once daily groups showed a rapid decrease starting at one week after dosing and remained decreased through 13 weeks in both studies.

For further information, please refer to the full prescribing information for tamsulosin hydrochloride [Flomax® (tamsulosin hydrochloride) Capsules, 0.4 mg US Package Insert, 2014, Flomax Relief® MR, 2014, and Tamsulosin hydrochloride, EU SmPC, 2013].

1.3 Summary of Key Safety Information for Study Drugs

1.3.1 Summary of Key Safety Information for Mirabegron

Mirabegron was first approved in Japan on 1 July 2011, and was launched to market on 16 September 2011 under the trade name Betanis®. On 28 June 2012, mirabegron received approval in the United States (trade name: Myrbetriq®). The approved indication is the treatment of OAB with symptoms of urinary incontinence, urgency, and urinary frequency. On 20 December 2012, mirabegron received marketing approval in the EU under the trade name Betmiga®. On 6 March 2013, mirabegron received approval in Canada (trade name: Myrbetriq®). As of September 3, 2015, mirabegron has regulatory approval in 58 countries.

The safety of mirabegron treatment has been well characterized in 5,863 subjects in the phase 2/3 studies, including 5,648 subjects with OAB, treated with mirabegron at doses ranging from 25 to 200 mg once daily. Of the 5,648 subjects with OAB who received mirabegron, 1,572 subjects received mirabegron continuously for at least 6 months, 1,482 subjects for at least 9 months, and 622 for at least 1 year.

Important potential risks include QT prolongation with suprathreshold doses or in high-risk populations, increased heart rate, increased blood pressure, non-immediate cutaneous hypersensitivity reactions and exposure in utero. The potential risks of QT prolongation, increased heart rate, or increased blood pressure are greater with increasing exposure. The expected adverse drug reactions for mirabegron are presented in [Table 2](#). The approved therapeutic dose of mirabegron in the United States and Canada is 25 mg once daily which may be increased to 50 mg once daily based on individual patient efficacy and tolerability [Mirabegron US Package Insert, 2015 and Myrbetriq Canadian Monograph, March 2015]. In the EU the approved starting dose of mirabegron is 50 mg once daily [EU SmPC, 2015]. The favorable benefit risk profile of mirabegron is not expected to change over time.

A mean increase of approximately 1 bpm for pulse rate was observed in OAB patients who received mirabegron 50 mg. This magnitude of change was similar for both 12-week and long-term studies, for men and women, and in both the mirabegron and tolterodine (active control) treatment groups. In patients with OAB, categorical increases in pulse rate were noted more frequently with mirabegron and tolterodine than with placebo, with similar

changes observed for mirabegron 50 mg and tolterodine. Pulse increases were more pronounced in young subjects in comparison to older adults (age 55 years and greater) subjects. Changes in pulse were reversible upon discontinuation of treatment.

An approximate mean increase in 1 mmHg from baseline for SBP/DBP was observed in OAB patients who received mirabegron 50 mg compared with placebo. This magnitude of change was similar for both 12-week and long-term studies, for men and women, and in both the mirabegron and tolterodine treatment groups. TEAE and SAE related to hypertension were similar for mirabegron 50 mg, placebo, and tolterodine in the 12-week studies, and were similar for mirabegron and tolterodine in the long-term study. Blood pressure increases were more pronounced in young subjects in comparison to older adult (age 55 years and greater) subjects. Changes in blood pressure were reversible upon discontinuation of treatment. Please refer to the product insert for expected adverse drug reactions (ADR).

Detailed information on the clinical safety profile for mirabegron can be found in the full prescribing information [Mirabegron US Package Insert, 2015, Myrbetriq Canadian Monograph, March 2015, and EU SmPC, 2015].

According to current package inserts, no dose adjustment is necessary for older adult patients. The pharmacokinetics of mirabegron is not significantly influenced by age. The C_{max} and AUC of mirabegron following multiple oral doses in older adult volunteers (≥ 65 years) were similar to those in younger volunteers (18 to 45 years). Of 5,648 patients who received mirabegron in the phase 2 and 3 studies, 2,029 (35.9%) were 65 years of age or older, and 557 (9.9%) were 75 years of age or older. No overall differences in safety or effectiveness were observed between patients younger than 65 years of age and those 65 years of age or older in the studies [Mirabegron US Package Insert, 2015 and Myrbetriq Canadian Monograph, March 2015, EU SmPC, 2015].

1.3.2 Summary of Key Safety Information for Tamsulosin Hydrochloride

In the phase 3 trials (178-CL-046, 178-CL-047, 178-CL-074), 308 men were on tamsulosin hydrochloride across treatment groups. There were no differences in rates of hypertension or elevated heart rate between men on and off tamsulosin hydrochloride.

1.3.3 Summary of Key Safety Information for Combination of Mirabegron and Tamsulosin Hydrochloride

Study 178-CL-080 was an open-label, 2-treatment arm, 2-sequence study to investigate the cardiovascular (CV) interactions between mirabegron (100 mg) and tamsulosin hydrochloride (0.4 mg as a single dose) in healthy male volunteers. Under the conditions of the study, the CV results suggest there is no clinically relevant pharmacodynamic interaction between tamsulosin hydrochloride and mirabegron. Combination treatment of mirabegron and tamsulosin hydrochloride did not appear to affect the safety profiles of either drug. In this interaction study, there were no serious adverse events and no events of syncope in either treatment arm.

In Japanese men with OAB induced by benign prostatic obstruction, addition of mirabegron to tamsulosin hydrochloride was shown to be more effective for ameliorating storage symptoms compared to tamsulosin hydrochloride monotherapy [Ichihara et al, 2014].

1.4 Risk-Benefit Assessment

Subjects randomized to placebo treatment are unlikely to benefit from the study beyond the benefits they receive from tamsulosin hydrochloride alone. However, OAB is not a life-threatening disease and it is not expected that a 12-week exposure to placebo treatment will have a negative impact on disease progress, given that subjects will have been on tamsulosin hydrochloride prior to study entry and it will be continued. Subjects receiving mirabegron are likely to benefit from at least a partial relief of symptoms during the study.

There is extensive clinical experience with tamsulosin hydrochloride monotherapy in the treatment of BPH. Clinical equipoise is maintained in the study because an alpha blocker is considered standard treatment of men with BPH and because the subjects are continuing on their usual prescribed dose as opposed to being placed on a tamsulosin hydrochloride placebo.

Mirabegron has a distinct mechanism of action (beta-3 adrenergic agonist) compared with the current standard of care, primarily antimuscarinics, for the treatment of symptoms of OAB. Antimuscarinics have been studied concomitantly with alpha blockers and appear to be efficacious without added risk. Muscarinic antagonists and beta-3 adrenergic agonists modulate bladder function through distinct molecular pathways. Thus concomitant use of tamsulosin hydrochloride and mirabegron offers the possibility of enhancing efficacy in the treatment of men with BPH who have co-existing OAB.

2 STUDY OBJECTIVE(S), DESIGN, AND ENDPOINTS

2.1 Study Objectives

The primary objective is to study the efficacy of mirabegron versus placebo in men with OAB symptoms while taking tamsulosin hydrochloride for LUTS due to BPH.

The secondary objective is to assess safety and tolerability of mirabegron versus placebo in men with OAB symptoms while taking tamsulosin hydrochloride for LUTS due to BPH.

Other objectives are to assess patient reported outcomes (PROs) as measured by Symptom Bother and Total Health Related Quality of Life scores as assessed by the Overactive Bladder questionnaire (OAB-q), EQ-5D-5L, Patient Perception of Bladder Condition (PPBC), Patient Perception of Intensity of Urgency Scale (PPIUS), International Prostate Symptom Score (IPSS), and Treatment Satisfaction-Visual Analog Scale (TS-VAS).

2.2 Study Design and Dose Rationale

2.2.1 Study Design

This is a randomized, double-blind, placebo-controlled, parallel-group, multi-center study. Approximately 985 subjects will be enrolled at up to 100 study centers in North America and Europe.

At Screening (Visit 1), subjects will enter into a 4-week open label tamsulosin hydrochloride 0.4 mg QD run-in period prior to being randomized into the 12-week double-blind treatment period (Visit 2). At the conclusion of the 4-week tamsulosin hydrochloride run-in period, subjects will complete a 3-day diary just prior to Baseline (Visit 2). Approximately 7 days prior to Visit 2 subjects will receive a phone call reminding them about the diary and to answer any questions.

A training diary will be completed in the first 2 weeks of the tamsulosin hydrochloride run-in period. During this evaluation period at least one telephone contact will take place with the subject. Diaries will be completed at home, using the electronic patient-reported outcome (ePRO) device, for 3 consecutive days prior to each visit: Baseline (Visit 2), Week 4 (Visit 3), Week 8 (Visit 4), and Week 12/End of Treatment (Visit 5). Site staff will contact the subject approximately 7 days prior to the scheduled visit to remind the subject that they need to complete the electronic diary, review completion instructions and review changes to concomitant medications and adverse events (if applicable).

If subjects meet all entry criteria at the end of the tamsulosin hydrochloride run-in period, subjects will be randomized to 1 of 2 treatment groups (mirabegron or placebo) for 12 weeks of treatment in addition to the continuation of tamsulosin hydrochloride 0.4 mg QD. Those subjects randomized to mirabegron will start at 25 mg and will increase to 50 mg after 4 weeks. Those subjects randomized to placebo will start blinded product matched to the mirabegron 25 mg tablet and will increase to blinded product matched to 50 mg mirabegron after 4 weeks. Once a subject has increased dose, he will remain on that dose for the remainder of the study unless for safety reasons he is required to discontinue study drug.

Three days before Visits 2 (Baseline), 3 (Week 4), 4 (Week 8), and 5 (Week 12), subjects will complete a 3-day diary, using the electronic patient-reported outcome (ePRO) device in which they will record micturition frequency, urgency (PPIUS), incontinence and volume voided. In addition the diary will capture morning and evening blood pressure and pulse rate measurements via HBPM. At Visit 1, International Prostate Symptom Score (IPSS) will be completed. At Visits 2, 3, 4, and 5, subjects will complete the IPSS, EQ-5D-5L, OAB-q, PPBC, and TS-VAS. Maximum urinary flow (Q_{max}) will be measured at Visit 1 (Screening/tamsulosin hydrochloride run-in) and Visit 5 (Week 12/End of Treatment). Post-void residual volume (PVR) will be assessed at Screening/tamsulosin hydrochloride run-in (Visit 1), Baseline (Visit 2) and at Week 4 (Visit 3), Week 8 (Visit 4) and Week 12/End of Treatment (Visit 5). A follow-up phone call (Visit 6) will be conducted 4-weeks after End of Treatment (Visit 5). Total study participation is approximately 20 weeks.

2.2.2 Dose Rationale

The approved dose in the treatment of overactive bladder in the United States and Canada is mirabegron 25 mg daily, which may be increased to 50 mg daily based on individual efficacy and tolerability [Mirabegron US Package Insert, 2015 and Myrbetriq Canadian Monograph, March 2013]. The recommended dose of mirabegron in the European SmPC is 50 mg [EU SmPC, 2015]. The dosing regimen for the study is starting with mirabegron 25 mg with an obligatory increase to mirabegron 50 mg after 4 weeks of treatment which is intended to reflect a pragmatic and clinically plausible regimen. The treatment effect size at Week 4 in the phase 3a program approaches the maximum treatment response for incontinence and micturition.

2.3 Endpoints

2.3.1 Primary Endpoints

The primary endpoint is:

- Change from Baseline (Visit 2) to Week 12/ End of Treatment (Visit 5) in mean number of micturitions per day based on a 3-day diary.

2.3.2 Secondary Endpoints

The secondary endpoints are:

- Change from Baseline (Visit 2) to Week 4, Week 8, and Week 12/End of Treatment (Visit 5) in mean volume voided per micturition.
- Change from Baseline (Visit 2) to Week 4, Week 8, and Week 12/End of Treatment (Visit 5) in mean number of incontinence episodes per day (FAS-I).
- Change from Baseline (Visit 2) to Week 4, Week 8, and Week 12/End of Treatment (Visit 5) in mean number of urgency episodes (grade 3 and 4) per day.
- Change from Baseline (Visit 2) to Week 4, Week 8, and Week 12/End of Treatment (Visit 5) in IPSS total score and subscales (Voiding, Storage, and Quality of Life).
- Change from Baseline (Visit 2) to Week 4, Week 8, and Week 12/End of Treatment (Visit 5) in mean number of urgency incontinence episodes per day (FAS-I).
- Change from Baseline (Visit 2) to Week 4, Week 8, and Week 12/End of Treatment (Visit 5) in Symptom Bother Total Health Related Quality of Life and subscale (coping, concern, sleep, social interaction, and symptom bother) scores as assessed by OAB-q questionnaire.
- Change from Baseline (Visit 2) to Week 4, Week 8, and Week 12/End of Treatment (Visit 5) as assessed by EQ-5D-5L questionnaire.
- Change from Baseline (Visit 2) to Week 4, Week 8, and Week 12/End of Treatment (Visit 5) in PPBC.
- Change from Baseline (Visit 2) to Week 4, Week 8, and Week 12/End of Treatment (Visit 5) in Total Urgency and Frequency Score (TUFS) using PPIUS (Grade 3 or 4).
- Change from Baseline (Visit 2) to Week 4, Week 8, and Week 12/End of Treatment (Visit 5) in mean number of nocturia episodes per day.

- Change from Baseline (Visit 2) to Week 4, Week 8, and Week 12/End of Treatment (Visit 5) in TS-VAS scores.
- Change from Baseline (Visit 2) to Week 4, Week 8, and Week 12/End of Treatment (Visit 5) in the number of protective garments (e.g. absorbent pads, incontinence briefs, disposable underwear).

2.3.3 Exploratory Endpoint

The exploratory endpoint is:

- Performance of subgroup analyses by PSA cutoff scores for < 2, 2-4.

2.3.4 Safety Variables

The safety variables are:

- Incidence and severity of treatment emergent adverse events (TEAEs) including AEs of special interest (see Section [5.4.3.2](#)).
- Vital signs: sitting systolic and diastolic blood pressure and pulse rate (home blood pressure monitoring [HBPM] and office measurements).
- ECG parameters (heart rate, PR, RR, QRS, QT, QTcF intervals).
- Laboratory parameters (hematology, serum chemistry, including liver function tests, and urinalysis).
- Change in PVR and Qmax.

3 STUDY POPULATION

3.1 Selection of Study Population

The study will enroll men at least 40 years of age who have symptoms of overactive bladder while taking the α -blocker tamsulosin hydrochloride for Lower Urinary Tract Symptoms (LUTS) due to Benign Prostatic Hyperplasia (BPH). Six hundred forty (640) subjects will be randomized to 1 of 2 treatment groups in a 1:1 randomization (mirabegron or placebo); 320 randomized to mirabegron; 320 randomized to placebo.

3.2 Inclusion Criteria

Inclusion Criteria assessed at Visit 1 (Screening).

Subject is eligible for the study if all of the following apply:

1. Institutional Review Board (IRB)/Independent Ethics Committee (IEC)-approved written Informed Consent and privacy language as per national regulations (e.g., HIPAA Authorization for US sites) must be obtained from the subject or legally authorized representative prior to any study-related procedures (including withdrawal of prohibited medication, if applicable).
2. Men ≥ 40 years of age with history of OAB symptoms (urinary frequency and urgency with or without incontinence) while taking tamsulosin hydrochloride 0.4 mg daily for at least 2 months to treat LUTS due to BPH.

3. Subject has symptoms of OAB (frequency of ≥ 8 micturitions per day and urgency episodes of ≥ 2 per day) for ≥ 3 months prior to Screening.
4. Subject has an IPSS score ≥ 8 .
5. Subject has Prostate-Specific Antigen (PSA) < 4 ng/mL OR PSA ≥ 4 but < 10 ng/mL with a prostate biopsy that is negative for cancer in the past two years.
6. Subject is willing and able to complete the 3-day diary (including urine volumes, vital sign measurements), and Quality of Life questionnaires.
7. Subject and their spouses/partners who are of childbearing potential must be using a highly effective method of birth control, which includes established use of oral, injected or implanted hormonal methods of contraception, placement of an IUD or IUS. Birth control must be practiced from Screening and continue throughout the study and for 30 days after the final study drug administration. In addition, sperm donation will not be allowed throughout the study and for 30 days after the final study drug administration.
8. Subject agrees not to participate in another interventional study while on treatment.

Inclusion Criteria assessed at Visit 2 (Baseline) based on the 3-day diary:

9. Subject continues to meet all inclusion criteria of Visit 1 (Screening).
10. Subject must experience an average of 8 or more micturitions per day over the 3-day diary period.
11. Subject must experience an average of 2 or more episodes of urgency per day (grade 3 or 4) over the 3-day diary period.

Waivers to the inclusion criteria will **NOT** be allowed.

3.3 Exclusion Criteria

Exclusion Criteria assessed at Visit 1 (Screening).

Subject will be excluded from participation if any of the following apply:

1. Subject has PVR > 200 mL.
2. Subject has $Q_{\max} < 5.0$ mL/second with a minimum voided volume of 125 mL.
3. Subject has hematuria > 3 rbc/hpf that has not been fully evaluated.
4. Subject has evidence of Urinary Tract Infection (UTI). Urine culture and sensitivity will be performed for positive leukocytes, nitrites, or turbidity, or at the Investigator's discretion, and will be confirmed with a culture greater than 100,000 cfu/mL. If a subject has a UTI, at Screening (Visit 1) the subject may be rescreened after successful treatment of the UTI (confirmed by a laboratory result of negative urine culture).
5. Subject has neurogenic bladder (spinal cord injury, multiple sclerosis, Parkinson's etc.).
6. Subject has diabetic neuropathy.

7. Previous open, robotic or minimally invasive prostate surgery (including transurethral procedures). Planned (scheduled) pelvic or prostate surgery planned during the study period.
8. Planned (scheduled) cataract or glaucoma surgery during the study period.
9. Subject with significant stress incontinence as determined by the Investigator.
10. Subject with clinically significant bladder outlet obstruction as determined by the Investigator.
11. Subject has an indwelling catheter or practices intermittent self-catheterization.
12. Subject has experienced 3 or more episodes of recurrent urinary tract infection within the last 12 months.
13. Subject has a symptomatic urinary tract infection, prostatitis, chronic inflammation such as interstitial cystitis, bladder stones, previous pelvic radiation therapy, or previous or current malignant disease of the pelvic organs (i.e., within the confines of the pelvis including the bladder, prostate and rectum; organs of the lower gastrointestinal tract are not necessarily considered pelvic organs as the distal ascending colon, the full transverse colon and proximal portion of the descending colon are in the abdomen).
14. Subject has received intravesical injection in the past 12 months with botulinum toxin, resiniferatoxin, or capsaicin.
15. Subject has ever received electro-stimulation therapy for OAB (e.g., sacral nerve stimulation or Percutaneous Tibial Nerve Stimulation [PTNS]).
16. Subject began or has changed a bladder training program or pelvic floor exercises less than 30 days prior to Screening.
17. Subject has postural hypotension or syncope or postural orthostatic tachycardia.
18. Subject has moderate or severe hepatic impairment defined as Child-Pugh Class B or C.
19. Subject has severe renal impairment defined as estimated creatinine clearance less than 29 mL/min/1.73 m² as determined by central laboratory calculation of eGFR. A subject with End Stage Renal Disease (ESRD) or undergoing dialysis is also not a candidate for the study.
20. Subject has severe uncontrolled hypertension, which is defined as a sitting systolic blood pressure ≥ 180 mmHg and/or diastolic blood pressure ≥ 110 mmHg.
21. Subject has baseline resting pulse rate < 60 BPM or > 90 BPM.
22. Subject has evidence of QT prolongation on Screening (Visit 1) or Baseline (Visit 2) electrocardiogram (ECG) defined as QTcF > 450 msec.
23. Subject has a clinically significant ECG abnormality, as determined by the Investigator.
24. Subject has AST or ALT $> 2x$ upper limit of normal (ULN), or γ -GT $> 3x$ ULN and considered clinically significant by the Investigator.

25. Subject has a hypersensitivity to any components of mirabegron, tamsulosin hydrochloride, or any of the inactive ingredients.
26. Subject has a history of angioedema.
27. Subject has any clinically significant condition, which in the opinion of the Investigator makes the subject unsuitable for study participation.
28. Subject has been treated with an experimental device within 28 days or received an investigational agent within 28 days or 5 half-lives, whichever is longer, prior to Screening.
29. Subject has a concurrent malignancy or history of any malignancy (within the past 5 years), except non-metastatic basal or squamous cell carcinoma of the skin that has been treated successfully.
30. Subject has ongoing alcohol and/or drug abuse.
31. Subject is using prohibited medications defined in [Appendix 1](#) Part A within 30 days prior to Screening (Visit 1) through Follow-Up Phone Call (Visit 6).
32. Subject has stopped, started or changed the dose of a restricted medication (defined in [Appendix 1](#) Part B) within the 30 days prior to Screening (Visit 1) through Follow-Up Phone Call (Visit 6).
33. Subject has participated in an interventional trial within 30 days prior to Screening (Visit 1).
34. Subject is involved in the conduct of the study as an employee of the Astellas group, third party associated with the study, or the study site team.
35. Subject has previously received mirabegron in the 6 months prior to Screening (Visit 1).

Exclusion Criteria assessed at Visit 2 (Baseline):

36. Subject was non-compliant during the 4-week tamsulosin hydrochloride run-in period, defined as taking less than 80% or greater than 120% of study medication.
37. Subject had an average total daily urine volume >3000 mL as recorded in the 3-day diary.

Waivers to the exclusion criteria will NOT be allowed.

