1.2.1.2 Summary of the Pharmacokinetics of Mirabegron

After oral administration of mirabegron in healthy volunteers, peak mirabegron plasma concentrations were attained between 3 to 5 hours. The absolute bioavailability increases from 29% at a dose of 25 mg to 45% at a dose of 150 mg under fasted conditions in healthy volunteers. Mean C_{max} and AUC_{inf} increased more than dose proportionality over the recommended dose range. Steady state concentrations were achieved within 7 days of once daily dosing with mirabegron. The C_{max} and AUC_{tau} of mirabegron and its metabolites following multiple oral doses in older adult subjects (≥ 65 years) were similar in those in younger subjects (18 to 45 years). The C_{max} and AUC_{tau} of mirabegron were approximately 40-60% higher in females than in males. The mean terminal $t_{1/2}$ is comparable in both sexes. Evaluation of special populations in the phase 1 studies demonstrated that volunteers with severe renal impairment (CrCL 15 to 29 mL/min or eGFR 15 to 29 mL/min per $1.73 m^2$) or moderate hepatic impairment (Child-Pugh Class B) had an approximately 2-fold increase in exposure to mirabegron relative to normal healthy volunteers.

The in vitro oxidative metabolism of mirabegron in human liver microsomes is primarily mediated by cytochrome P450 (CYP) 3A4, but a possible role for CYP2D6 could not be excluded. In vitro CYP inhibition studies suggest that mirabegron is a moderate and time-dependent inhibitor of CYP2D6 and a weak inhibitor of CYP3A4.

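### Exclusion criterion 19 stops at eGFR below 29, so a man at exactly 29, inside the range the protocol elsewhere calls severe renal impairment, passes the numeric rule

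*Protocol*

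**What the plan says.** Criterion 19 in Section 3.3 reads: "Subject has severe renal impairment defined as estimated creatinine clearance less than 29" mL/min/1.73 m², on the eGFR that the central laboratory calculates. The synopsis carries the same rule. The next sentence of the criterion adds: "A subject with End Stage Renal Disease (ESRD) or undergoing dialysis is also not a candidate for the study". Section 3.3 allows no waivers of the exclusion criteria.

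Section 1.2.1.2 summarises the phase 1 work in special populations. It refers to "volunteers with severe renal impairment (CrCL 15 to 29 mL/min or eGFR 15 to 29 mL/min per" 1.73 m² and to volunteers with moderate hepatic impairment (Child-Pugh Class B), and says that these groups "had an approximately 2-fold increase in exposure to mirabegron relative to normal healthy volunteers".

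Three other statements bear on the point:

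- Section 1.3.1: "The potential risks of QT prolongation, increased heart rate, or increased blood pressure are greater with increasing exposure".
- Section 2.2.2, on the dosing regimen: "obligatory increase to mirabegron 50 mg after 4 weeks of treatment". Section 5.1.2 provides no dose reduction after that step. The only departure is to stop study drug for safety reasons.
- Criterion 27 is the general backstop: "Subject has any clinically significant condition, which in the opinion of the Investigator makes the subject unsuitable for study participation".

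**The concern.** The protocol gives one term two upper limits. In the background section, severe renal impairment runs up to and includes 29. In the eligibility rule it ends just short of 29. The number is the same in both places and only the operator differs, so a boundary slip is the most natural explanation. No section gives a reason for admitting a man at 29.

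The neighbouring criterion supports that reading. The exposure sentence in Section 1.2.1.2 names two groups, severe renal impairment and Child-Pugh Class B. Criterion 18 excludes Child-Pugh Class B completely. Criterion 19 excludes the renal group except for its top value.

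What is at stake is a safety exclusion. The protocol ties the QT, heart-rate and blood-pressure risks to exposure, makes the move to 50 mg compulsory and has no step back down. Eligibility is therefore the main place where raised exposure from poor renal function is controlled, and sites may not waive the number.

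**Working it through.** No sample size, power or error rate enters this point. The check applies the rule in criterion 19 to the range in Section 1.2.1.2.

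**Inputs**

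- Rule (Section 3.3 and synopsis, criterion 19): excluded if eGFR < 29 mL/min/1.73 m².
- Range described as severe (Section 1.2.1.2): 15 ≤ eGFR ≤ 29.
- Randomized men (Sections 3.1 and 7.1): 640, of whom 320 on mirabegron.

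**Step 1. Apply the rule value by value**

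| eGFR | Criterion 19 as written | Severe in Section 1.2.1.2? |
|---|---|---|
| 15 | excluded | yes |
| 28 | excluded | yes |
| 28.9 | excluded | yes |
| 29 | passes | yes |
| 29.5 | passes | not assigned |
| 30 | passes | no |

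The two statements disagree at exactly one point, eGFR 29. Values above 29 and below 30 also pass, but the protocol does not place them in the severe range.

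**Step 2. Count the whole-number values**

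- In the severe range: 29 − 15 + 1 = 15.
- Excluded by < 29: 15 to 28, which is 28 − 15 + 1 = 14.
- Not excluded: 15 − 14 = 1, the value 29.

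**Step 3. Look for another rule that catches him**

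- The sentence on ESRD and dialysis does not cover a man with eGFR 29 who is not on dialysis.
- No other criterion sets a renal cut-off.
- Criterion 27 can exclude him, but only by the individual investigator's judgement.

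**Step 4. Headcount, by assumption only**

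The protocol gives no eGFR distribution. Suppose that between 0.05% and 0.5% of otherwise eligible men have eGFR 29. This range is assumed and does not come from the document.

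- Of all randomized: 640 × 0.0005 = 0.32, and 640 × 0.005 = 3.2.
- On mirabegron: 320 × 0.0005 = 0.16, and 320 × 0.005 = 1.6.

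**Step 5. Test the correction**

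With < 30 or with ≤ 29, no whole number from 15 to 29 passes. If the laboratory reports decimals the two differ: < 30 also excludes 29.1 to 29.9, and ≤ 29 does not.

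**The case against.** The strongest reply is that there is no true contradiction. Section 1.2.1.2 describes volunteers in earlier phase 1 studies. It does not define eligibility for this trial. Criterion 19 supplies its own working definition, identical in both places, so sites and the laboratory have one unambiguous rule, and nothing says it must reproduce the phase 1 range.

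The safety argument can also be pressed back:

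- The doubling of exposure is a figure for the severe group as a whole. None is given at 29, and nothing in the protocol shows that a man at 29 is at higher risk than a man at 30.
- Sections 1.2.1.3 and 1.3.1 say that doses of 25 to 200 mg were studied in OAB patients, so doubled exposure at 50 mg plausibly lies within what has been seen.
- The label summaries in Section 1.2.1.3 advise against use in end stage renal disease and do not name severe renal impairment, so the exclusion is already stricter than the labels as summarised.
- Criteria 20 to 22 screen out severe hypertension, a resting pulse outside 60 to 90 and QTcF above 450 msec. Office vital signs, ECG and creatinine are repeated at every treatment visit.

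Much of this stands. The safety concern is limited, no hazard at 29 is demonstrated, and the headcount is an assumption. It does not remove the mismatch. The 15 to 29 range is the protocol's only evidence on exposure in severe renal impairment, which makes it the natural reference for a cut-off aimed at that condition. A numeric central-laboratory rule exists so that the decision does not depend on each investigator's judgement.

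**Conclusion.** The point holds, at the lowest level of importance. As written, criterion 19 leaves out the top value of the range it appears to be aimed at: 1 whole-number value of 15. This rests on taking Section 1.2.1.2 as the reference for what severe means. That is an inference about intent, though no other numeric description of the term is offered. Under the assumed prevalence, at most about three randomized men would be affected, and possibly none. Sample size, blinding and the primary analysis do not change. The reason to act is consistency in a safety exclusion, not a demonstrated risk to participants.

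**What to change.** In criterion 19, in both Section 3.3 and the synopsis, set the threshold to eGFR < 30 mL/min/1.73 m² by central laboratory. If the laboratory reports whole numbers, ≤ 29 does the same. If it reports decimals, < 30 additionally excludes values between 29 and 30, which the protocol does not call severe, and ≤ 29 is the narrowest correction that agrees with Section 1.2.1.2. Align any eligibility flag the central laboratory uses.

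In the same line, creatinine clearance can be replaced by eGFR. That is editorial only, since the criterion already fixes the laboratory eGFR as the measure.

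The cost is one line in each of two places, plus the flag if there is one. The effect on recruitment is negligible.
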